## 7.2 Medical History

Medical history data will be coded using the Medical Dictionary for Regulatory Activities (MedDRA). The actual version of the MedDRA coding dictionary will be noted in the statistical tables and clinical study report. The number and percentage of subjects in each medical history category (by MedDRA system organ class (SOC) and preferred term (PT)) will be summarized. The SOCs will be presented in alphabetical order, and the PTs will be presented in alphabetical order within each SOC. Subjects reporting more than one PT within a SOC will be counted only once for that SOC.

### 7.3 Prior, Concomitant, and Post-Treatment Medications

A prior medication is defined as any medication taken prior to the date of the first dose of study treatment (GLE/PIB). A concomitant medication is defined as any medication that started prior to the date of the first dose of study treatment and continued to be taken on or after the first dose of study treatment or any medication that started on or after the date of the first dose of study treatment, but not after the date of the last dose of study treatment. A post-treatment medication for the treatment of HCV is defined as any medication started on or after the date of last dose of study treatment with the indication entered as "Hepatitis C."

Prior medications will be divided into the following categories:

- HCV medications taken for the most recent prior HCV infection;
- Prior HIV medications taken by subjects with HCV/HIV co-infection at baseline;

- Non-prescribed illicit drugs overall and by injection or non-injection route and specific route within injection and non-injection routes;
- Opiate substitution therapy medications;
- All other prior medications.

Concomitant medications will be divided into the following categories:

- Concomitant HIV medications taken by subjects with HCV/HIV co-infection at baseline;
- Non-prescribed illicit drugs overall and by injection or non-injection route and specific route within injection and non-injection routes;
- Opiate substitution therapy medications;
- All other concomitant medications.

The number and percentage of subjects taking prior medications, concomitant medications, and post-treatment HCV medications will be summarized by generic drug name based on the World Health Organization (WHO) Drug Dictionary. Opiate substitution therapy and non-prescribed illicit drugs will be summarized as reported.

## 8.0 Handling of Potential Intercurrent Events for the Primary and Key Secondary Endpoints

The primary efficacy endpoint of achievement of SVR12 will be analyzed based on the ITT population, and any subject who discontinues the study with an unknown SVR12 status (after applying backward imputation) will be counted as a failure for SVR12. The key secondary efficacy endpoint of achievement of SVR12 will be analyzed based on the mITT-VF population, and intercurrent events will not have an effect on this analysis.

## 9.0 Efficacy Analyses

## 9.1 General Considerations

All tests and CIs will be two-sided at an alpha level of 0.05.

All efficacy analyses will be performed on the ITT population, unless otherwise specified.

Missing data will be imputed as described in Section 9.2 for analyses of the HCV RNA endpoints of SVR and virologic failure and the patient reported outcomes (PROs) questionnaires.

If a subject starts another treatment for HCV, then all HCV RNA and PRO values for this subject measured on or after the start date of the new HCV treatment will be excluded from analyses. The subject will be considered a failure for summaries of SVR at all time points after the start of the new HCV treatment.

Plasma HCV RNA levels will be determined for each sample collected by the central laboratory using the Roche COBAS® AmpliPrep/COBAS® TaqMan® Quantitative HCV Test, v2.0. The lower limit of detection (LLOD) and lower limit of quantification (LLOQ) for this assay (regardless of genotype) are both 15 IU/mL.

### **Definitions for Efficacy Endpoints**

A confirmed quantifiable value during treatment is defined as any two consecutive HCV RNA measurements  $\geq$  LLOQ (or 100 IU/mL for **Breakthrough**), either both during treatment or at the final treatment measurement and the next consecutive post-treatment measurement. A confirmed quantifiable post-treatment value is defined as any two consecutive post-treatment HCV RNA measurements  $\geq$  LLOQ.

**Breakthrough** confirmed HCV RNA  $\geq$  100 IU/mL after HCV RNA < LLOQ during the Treatment Period; or confirmed increase from nadir in HCV RNA (two consecutive HCV RNA measurements > 1 log10 IU/mL above nadir) at any time point during the Treatment Period. A single breakthrough value ( $\geq$  100 IU/mL or > 1 log10 above nadir)

followed by lost to follow-up also will be considered a breakthrough (i.e., will not require confirmation).

**EOT failure** HCV RNA  $\geq$  LLOQ at end of treatment with at least 6 weeks of treatment, where the HCV RNA value must be collected on or after Study Treatment Day 36 and study treatment duration  $\geq$  36 days.

**On-Treatment Virologic Failure** Breakthrough or EOT Failure; if a subject meets both definitions of Breakthrough and EOT Failure, he or she will be categorized as Breakthrough only.

**SVR**4 HCV RNA < LLOQ in the SVR4 window (4 weeks after the last actual dose of study treatment) without any confirmed quantifiable ( $\geq$  LLOQ) post-treatment value before or during that SVR window.

**SVR**12 HCV RNA < LLOQ in the SVR12 window (12 weeks after the last actual dose of study treatment) without any confirmed quantifiable ( $\geq$  LLOQ) post-treatment value before or during that SVR window.

**Relapse**12 confirmed HCV RNA  $\geq$  LLOQ between end of treatment and 12 weeks after last actual dose of study treatment (up to and including the SVR12 assessment time point) for a subject with HCV RNA < LLOQ at Final Treatment Visit who completed treatment and has post treatment HCV RNA data available, excluding reinfection as described below.

**Relapse**overall confirmed HCV RNA  $\geq$  LLOQ between end of treatment and up to and including the last HCV RNA measurement collected in the PT Period for a subject with HCV RNA < LLOQ at Final Treatment Visit who completed treatment and has post treatment HCV RNA data available, excluding reinfection as described below.

**Virologic failure through Post-Treatment Week 12** SVR12 non-responders who experience on-treatment virologic failure or Relapse12.

Only subjects who have at least one post-treatment HCV RNA value will be included in analyses of relapse. For relapse analyses, the completion of treatment is defined as a study treatment duration  $\geq$  52 days. If the last available post-treatment value is  $\geq$  LLOQ, then the subject will be considered a relapse (i.e., will not require confirmation).

HCV reinfection is defined as confirmed HCV RNA  $\geq$  LLOQ after the end of treatment in a subject who had HCV RNA < LLOQ at Final Treatment Visit, along with the post-treatment detection of a different HCV genotype, subtype, or clade compared with baseline, as determined by phylogenetic analysis of the NS3 or NS5A, and/or NS5B gene sequences. Reinfection in the case of the same HCV subtype is defined as a clade switch, as indicated by the lack of clustering between the baseline and post-treatment sequences by phylogenetic analysis. If phylogenetic analysis is not possible due to technical difficulties, HCV reinfection may be determined with a confirmed HCV genotype or subtype switch by the Versant HCV Genotype Inno-LiPA Assay v2.0 or Sanger assay.

Post-treatment relapse is defined as described earlier (**Relapse**12 and **Relapse**overall), and no genotype, subtype, or clade switch compared with baseline as determined by phylogenetic analysis of the NS3 or NS5A gene sequences. If phylogenetic analysis is not possible due to technical difficulties, the subject will be defined as having a post-treatment relapse unless an HCV genotype or subtype switch is confirmed by the Versant HCV Genotype Inno-LiPA Assay v2.0 or Sanger assay.

#### Reasons for SVR12 Non-Response

Subjects who do not achieve  $SVR_{12}$  ( $SVR_{12}$  non-responders) will be categorized as having:

- 1. On-treatment virologic failure (see **On-treatment virologic failure** definition);
- 2. HCV reinfection (see definition described earlier);
- 3. Relapse12 (see **Relapse12** definition);

- Prematurely discontinued study treatment with no on-treatment virologic failure (defined as any SVR12 non-responder who prematurely discontinued study treatment [study treatment duration < 52 days] and did not meet the **On-treatment** virologic failure or HCV reinfection definitions);
- 5. Missing follow-up data in the SVR12 window (defined as any subject who completed study treatment without data in the SVR12 window after applying the imputation rules and not meeting the definitions of [1], [2], [3], or [4]);
- Other (defined as any SVR12 non-responder not meeting the definitions of [1] [5]).

For the reasons for  $SVR_{12}$  nonresponse defined above, subjects are only to be counted in 1 category. Specifically, subjects who were  $SVR_{12}$  non-responders meeting the definition of HCV reinfection will be counted in the reinfection category regardless of whether they meet the definition of prematurely discontinued study treatment or Relapse12.

## 9.2 Handling of Missing Data

### **Missing Data Imputation for SVR**

For analyses of SVR, subjects missing visit values will have backward imputation applied, if possible. For backward imputation, if the nearest HCV RNA value after the SVR window is unquantifiable or undetectable, then it will be used to impute the HCV RNA value in the SVR window. If a subject is missing an HCV RNA value within the appropriate SVR window after performing backward imputation, then this value will be imputed with an HCV RNA value from a local laboratory if present; otherwise, the HCV RNA value will be missing. A subject with missing HCV RNA data in the analysis window, after imputations, will be imputed as a failure.

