#### 2.5 Sample Size Determination

The threshold for comparison for the primary efficacy estimand will be derived from a weighted average of the ITT SVR12 rates in the PWID and non-PWID chronically infected populations of subjects who received GLE/PIB in Phase 2 and 3 trials. As presented in the

Mavyret US Prescribing Information 2020, Section 14.9, the ITT SVR12 rate among chronically infected HCV PWID (current/recent PWID) is 88.7% and is 97.8% among chronic non-PWID (former/non-PWID). The threshold for comparison will be calculated by (proportion of PWID in the ITT population of this study  $\times$  88.7%) + (proportion of non-PWID in the ITT population of this study  $\times$  97.8%) minus a margin of 6%. Therefore, the threshold would be 82.7% if all subjects in the ITT population of this study are PWID, and it would be 91.8% if all subjects in the ITT population of this study are non-PWID. Similarly, the threshold for the comparison of the key secondary estimated will be derived from a weighted average of the mITT-VF SVR12 rates in the PWID and non-PWID chronically infected populations. The mITT-VF SVR12 rate among chronically infected HCV PWID is 98.2% and is 98.8% among chronic non-PWID. The threshold for comparison will be calculated by (proportion of PWID in the mITT-VF population of this study  $\times$  98.2%) + (proportion of non-PWID in the mITT-VF population of this study  $\times$  98.8%) minus a margin of 6%. It follows that the threshold would be 92.2% if all subjects in the mITT-VF population of this study are PWID, and it would be 92.8% if all subjects in the mITT-VF population of this study are non-PWID.

It is planned to enroll approximately 283 subjects. Assuming all of the subjects in the ITT population of this study are PWID, 283 subjects will provide 80% power to show that an 88.7% SVR12 rate among acutely infected HCV subjects in the ITT population is superior to a threshold of 82.7% based on the historical ITT SVR12 rate among chronically infected HCV subjects, using a two-sided 95% CI. Assuming all of the subjects in the ITT population of this study are non-PWID, 283 subjects will provide greater than 95% power to show that a 97.8% SVR12 rate among acutely infected HCV subjects in the ITT population is superior to a threshold of 91.8% based on the historical ITT SVR12 rate among chronically infected HCV subjects.

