## 4.0 Analysis Populations

The following population sets will be used for the analyses.

The ITT population is defined as all enrolled subjects who received at least 1 dose of study treatment. The ITT population will be used for the primary efficacy analysis and other secondary efficacy analyses.

The mITT-VF population is defined as all enrolled subjects who received at least 1 dose of study treatment, excluding those who did not achieve SVR12 for reasons other than virologic failure (i.e., those with HCV reinfection, those who did not achieve SVR12 due to early premature discontinuation of study treatment, and those who were missing HCV RNA data in the SVR12 window after backward imputation). The mITT-VF population will be used for the key secondary efficacy analysis.

The Safety Analysis Set consists of all subjects who received at least 1 dose of study treatment.

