## 9.5 Additional Efficacy Analyses

The following additional efficacy endpoints will be summarized for the ITT population:

- At each post-baseline visit in the Treatment Period, achievement of HCV RNA < LLOQ (using data as observed);
- Achievement of SVR4 (as defined in Section 9.1);
- Virologic failure through Post-Treatment Week 12 (as defined in Section 9.1);
- Relapseoverall (as defined in Section 9.1).

For each of the endpoints above, the number and percentage of subjects meeting the endpoint will be calculated. For the endpoints of SVR4 and virologic failure, a two-sided 95% CI will be calculated using Wilson's score method. Imputations for missing data will be performed as described in Section 9.2 for analysis of SVR4, where a missing response will be imputed as a failure after performing the described imputation. All other endpoints will be presented using data as observed.

A summary of the subjects in the ITT population who completed treatment and relapsed (defined as **Relapse**overall) will be prepared displaying the number of subjects relapsing overall and by SVR visit window (within the SVR4 or SVR12 window or after SVR12 window), including the subject number and the SVR visit window corresponding to the first HCV RNA value of those indicating the occurrence of relapse. A similar summary will be prepared for subjects in the ITT population who prematurely discontinued treatment and relapsed after having HCV RNA < LLOQ at their Final Treatment Visit.

A listing of subjects in the ITT population excluded from the relapse denominator (e.g., study treatment duration < 52 days or no post-treatment HCV RNA) will be provided, as applicable.

The concordance between  $SVR_4$  and  $SVR_{12}$  will be assessed for the ITT population by the agreement between  $SVR_4$  and  $SVR_{12}$  and the positive predictive value (PPV) and negative predictive value (NPV) of  $SVR_4$  on  $SVR_{12}$ . The agreement between  $SVR_4$  and  $SVR_{12}$  is a percentage defined as the number of subjects achieving both  $SVR_4$  and  $SVR_{12}$  and the

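### For some completers with no HCV RNA value in the SVR12 window, a later result decides mITT-VF membership: a late negative is kept as a success, a late same-virus positive is excluded as missing

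*SAP*

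**What the plan says.** Four parts of the SAP act together.

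- **SAP 9.2 (Missing Data Imputation for SVR).** A value after the window is carried back only if it is negative: "if the nearest HCV RNA value after the SVR window is unquantifiable or undetectable, then it will be used to impute" the window value. If the window is still empty, a local-laboratory value is used where there is one. Otherwise the subject counts as an SVR12 failure.
- **SAP 9.1 (definitions).** Relapse12 stops at the SVR12 assessment time point. Relapse_overall runs to the last post-treatment measurement.
- **SAP 9.1 (Reasons for SVR12 Non-Response).** Category 5, missing follow-up, takes completers with no data in the SVR12 "window after applying the imputation rules and not meeting the definitions of [1], [2], [3], or [4"]. Relapse_overall is not among the listed reasons.
- **SAP 4.0.** mITT-VF leaves out subjects who lack HCV RNA data in the SVR12 "window after backward imputation). The mITT-VF population will be used for the key secondary efficacy analysis". Late positives are not excepted.

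The SAP foresees relapse first seen late. SAP 9.5 tabulates Relapse_overall by window, with a row for after the SVR12 window, "including the subject number and the SVR visit window corresponding to the first HCV RNA value of those indicating the occurrence of relapse".

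**The concern.** mITT-VF is meant to leave out only subjects whose non-response has a cause other than virologic failure. Consider two completers with the same lapse in follow-up: no quantifiable post-treatment value so far, nothing in the SVR12 window, one sample afterwards. If the sample is negative, the subject is in the numerator and the denominator. If it is positive with the same virus, the subject is in neither. Within this narrow group, everyone who is kept is a success.

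This bears on a confirmatory claim, because the key secondary hypothesis is part of the fixed-sequence procedure in SAP 12.0. SAP 8.0 states that intercurrent events have no effect on the analysis, and none of the supplementary analyses in 9.4.3 varies this rule. The SAP also disagrees with itself: 9.7 treats Relapse_overall as virologic failure, so one subject can be a virologic failure for resistance sequencing and missing for the key secondary test.

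**Working it through.** **1. Tracing the subject.** The completer has at least 52 days of treatment, HCV RNA below LLOQ at end of treatment, no quantifiable post-treatment value before the window, and no central or local value in it.

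| Late sample | SAP 9.2 | SAP 9.1 reason | SAP 4.0 |
|---|---|---|---|
| < LLOQ | carried back | none (SVR12 achieved) | kept, success |
| ≥ LLOQ, same virus | not carried back | not Relapse12, so category 5 | excluded |

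In ITT the second subject is an SVR12 failure, so the primary analysis is not affected.

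**2. Reproducing the plan's power.** Inputs: "All tests and CIs will be two-sided at an alpha level of 0.05" (SAP 9.1); "It is planned to enroll approximately 283 subjects" (SAP 2.5); "the threshold would be 82.7% if all subjects in the ITT population of this study are PWID" (SAP 2.5); mITT-VF n = 255 with thresholds of 92.2% (all PWID) and 92.8% (all non-PWID).

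Wilson lower bound, with p = x/n and z = 1.96:

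L = [p + z²/2n − z√(p(1−p)/n + z²/4n²)] / (1 + z²/n)

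- ITT, 82.7%: 247/283 is the smallest passing count. Exact binomial power at 88.7% is 80.4%, which agrees with "283 subjects will provide 80% power to show that".
- mITT-VF, 92.2%: 244/255 passes (L = 92.44%) and 243/255 does not (91.96%), so at most 11 failures. Power at 98.2% is 99.7%.
- mITT-VF, 92.8%: at least 245/255, so at most 10 failures. Power at 98.8% is 99.97%.

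The plan states more than 95% for both mITT-VF cases. No stated figure is in dispute.

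**3. Restoring excluded subjects.** Assume a reported 250/255 (255 × 0.982 = 250.4). Put back k late same-virus positives as failures, giving 250/(255 + k):

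| k | Rate | Lower bound |
|---|---|---|
| 0 | 98.0% | 95.5% |
| 1 | 97.7% | 95.0% |
| 3 | 96.9% | 94.0% |
| 5 | 96.2% | 93.1% |
| 6 | 95.8% | 92.61% |
| 7 | 95.4% | 92.17% |

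The result reverses at k = 6 against 92.8% and at k = 7 against 92.2%. The first restored subject costs 250/255 − 250/256 = 0.38 points.

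**4. Upper bound on type I error.** Let 255 subjects have a true rate equal to the 92.2% threshold. Let m of them be late returners whose failures are all dropped. Then F2 ~ Bin(m, 0.078) is dropped and F1 ~ Bin(255 − m, 0.078) is kept. The test passes if 255 − F1 − F2 reaches the smallest passing count for n = 255 − F2. Summing over F2:

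| m (share of 255) | One-sided type I error |
|---|---|
| 0 | 1.88% |
| 5 (2%) | 2.30% |
| 8 (3%) | 2.59% |
| 13 (5%) | 3.15% |
| 26 (10%) | 5.14% |
| 51 (20%) | 12.06% |

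The nominal level is 2.5%. Counting the late positives as failures keeps it at 1.88%. The values of m are assumptions; the documents give no number of late returners.

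**The case against.** Much of the case on the other side stands, and it limits the point.

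- **Not all late returners.** A reader might infer that every late returner who stays in mITT-VF is a success by construction. The SAP does not support that. A confirmed post-treatment value needs two consecutive quantifiable measurements, and the second need not fall in the window. A quantifiable Post-Treatment Week 4 value followed by a late positive is therefore naturally read as Relapse12, and the subject stays as a failure. On-treatment virologic failures also stay, and a local-laboratory value in the window is used.
- **A competing reading.** SAP 9.1 says that a subject whose last post-treatment value is at or above LLOQ is considered a relapse. No time limit is repeated there. The sentence waives confirmation and does not clearly extend Relapse12, and SAP 4.0 makes no exception. Still, with 9.7 it makes this partly a conflict to settle.
- **Direction.** A reader might infer that the rule always raises the rate. It does so if the relapse began by Week 12. If it began later, a true SVR12 success is removed and the rate falls trivially (251/256 = 98.05% against 250/255 = 98.04%). The timing is not observed.
- **Rationale for the asymmetry.** A late negative is good evidence of no infection at Week 12. A late positive does not prove infection at Week 12. This is a sound argument against making the late positive a failure in the main analysis. It does not justify leaving an outcome-dependent exclusion untested.
- **Visibility.** The SAP 9.5 tabulation and the listing of ITT non-responders let a reader identify these subjects. They do not give the resulting mITT-VF rate and interval.

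**Conclusion.** The point holds for one narrow group: completers with no earlier quantifiable post-treatment value and no central or local value in the SVR12 window. For them, on the plain reading of SAP 4.0, 9.1 and 9.2, the late result decides mITT-VF membership. The effect tends to favour the key secondary rate when the relapse began by Week 12.

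The effect is probably small. The last scheduled visit is Post-Treatment Week 12 (Protocol Appendix D), and the SAP does not give day limits for the SVR12 window, so the number affected cannot be derived. Reversing an assumed 250/255 takes six or seven such subjects. The type I figures are upper bounds: they put the true rate at the threshold and drop every failure among late returners.

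Two further inferences are not supported. The primary analysis is not biased, because missing counts as failure in ITT. The endpoint of virologic failure through Post-Treatment Week 12 is not understated either: it is limited to Week 12 by definition, and later relapse has its own endpoint. This is an inexpensive improvement and does not threaten the trial's conclusion.

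**What to change.** 1. Reconcile SAP 4.0, 9.1, 9.2 and 9.7 on how to classify a completer with no SVR12-window value and a later same-virus positive. In particular, say whether the last-value sentence in 9.1 applies after the Relapse12 time limit.
2. Add to SAP 9.4.3 a supplementary mITT-VF analysis that keeps as virologic failures those subjects with Relapse_overall first seen after the SVR12 window, no genotype, subtype or clade switch, and sampling before any new HCV treatment. Use the same Wilson interval and a threshold weighted on the subjects included.

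The cost is a few sentences and one table. No new data are needed, since Relapse_overall is already derived. The downside is that a relapse that began after Week 12 would count as a failure. So would a reinfection that could not be sequenced: SAP 9.7 sequences only samples of at least 1000 IU/mL, and SAP 9.1 defaults to relapse when phylogenetic analysis is not possible and no genotype or subtype switch is confirmed. The supplementary rate may therefore be slightly less favourable, and the report should say so.
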